16. PHARMACOKINETICS

The pharmacokinetic (PK) concentration data will be summarized on the PK set for the subjects in the teduglutide treatment arm only. The descriptive statistics of PK concentration will be

Document:	\\quintiles.net\Enterprise\Apps\sasdata\SASa\sas\Shire\Teduglutide\Biostatistics\Documentation\SAP\TE D-C14-006_SAP_Final_V1.0_20170714		
Author:	PPD	Version Number:	Final V1.0
		Version Date:	14Jul2017

Template No: CS_TP_BS016 – Revision 3
Effective Date: 01May2012

Reference: CS_WI_BS005

Copyright © 2012 Quintiles Transnational Corp. All rights reserved.

The contents of this document are confidential and proprietary to Quintiles Transnational Corp. Unauthorized use, disclosure or reproduction is strictly prohibited.

summarized by treatment arm and dose group for each timepoint. The listings for PK concentration data will also be provided.

For the PK evaluation, blood will be collected at the clinic on day 0 when the subject receives the first dose of teduglutide. Blood sampling will occur at the following timepoints: predose and 1, 2, and 4 hours postdose.

- 0-hour (predose) draw: any time prior to the daily dose, on the day of dosing, but at least 14 hours after the previous dose (if the PK blood draw does not occur at day 0)
- 1-hour postdose draw: ± 10 minutes
- 2-hour postdose draw: ± 10 minutes
- 4-hour postdose draw: ± 30 minutes

If a subject is unable to provide blood samples at baseline (day 0) on the first day of treatment, then blood may be collected for PK analysis during any other future clinic visit while the subject is still receiving treatment with teduglutide.

The actual date and time of teduglutide administration and blood draw will be documented on the PK blood sampling eCRF.

Descriptive statistics (mean, median, standard deviation, minimum and maximum values) of PK concentration will be calculated to summarize the absolute values and change from predose at each timepoint. The PK parameters will be derived and estimated based on measured teduglutide plasma concentrations using a population PK modeling approach and will be described within a separate SAP.

17. EFFICACY OUTCOMES

Efficacy analyses for the primary efficacy endpoint, $\geq 20\%$ reduction in weight-normalized PN/IV volume between the baseline and week 24/EOT visit, will be performed using both diary and prescribed data on the ITT and PP analysis sets. All other efficacy analyses will be performed on the ITT analysis set only. Analyses based on diary data and prescribed data will be presented separately. The descriptive statistics of efficacy outcomes will be summarized by treatment arm and dose group. The listings for efficacy measures which are collected on the CRF forms will be provided.

Document:	\\quintiles.net\Enterprise\Apps\sasdata\SASa\sas\Shire\Teduglutide\Biostatistics\Documentation\SAP\TE D-C14-006_SAP_Final_V1.0_20170714		
Author:	PPD	Version Number:	Final V1.0
		Version Date:	14Jul2017
Template No:	CS_TP_BS016 – Revision 3	Reference:	CS_WI_BS005
Effective Date:	01May2012		

17.1. PRIMARY EFFICACY

17.1.1. PRIMARY EFFICACY VARIABLE & DERIVATION

The primary efficacy variable is weight-normalized reduction in PN/IV volume of at least 20% at EOT compared to baseline. This will be analyzed in two ways: 1) based on the subject diary data (also referred to as “actual”), and 2) based on the investigator-prescribed data (referred to as “prescribed”). PN/IV support will be reported in both subject diary data and the investigator-prescribed data in the eCRF. Investigator-prescribed data are the most recent PN/IV prescription (from either baseline or prescription adjustments) prior to or on the date of visit, captured in the PN/IV history and PN/IV adjustments eCRFs. PN/IV diary data are collected over 24-hour periods that start on the assigned date. Depending on the time of day at which the 24 hour period begins, which can vary by subject, overnight PN/IV infusion volumes after midnight may be associated with prior the date. Baseline actual PN/IV parameters will be calculated using all the diary data collected within 14 days prior to the first dose or baseline visit. Calculation of post-baseline actual PN/IV parameters will be based on the daily support recorded in subjects’ diaries within 7 days prior to the date of each scheduled post-baseline visit. Week 1 calculations will exclude any pre-baseline diary data. The calculation of actual PN/IV volume normalized to weight will follow the formula below:

$$\text{Average daily value} = [(\text{sum of non-missing daily values in the diary} / \text{number of days with non-missing values})] / \text{last available body weight prior to the visit}$$

If more than 2 days’ values in a week are missing, the average daily value will not be calculated and will be assigned as missing. The same strategy will be used to calculate all other average diary parameters, including PN/IV calories, PN/IV hours per day, EN volume, and EN calories. If more than 5 days’ values in two weeks before baseline visit, the baseline values are missing.

The calculation of prescribed PN/IV volume normalized to weight will follow the formula below:

$$\text{Average daily value} = (\text{prescribed weekly PN/IV volume} / 7) / \text{last available weight prior to or on the date of visit}$$

An analogous strategy will be used to calculate other prescribed parameters, including PN/IV calories, PN/IV hours per day, EN volume, and EN calories.

Percent reduction in weight-normalized actual and prescribed PN/IV volume from baseline at the scheduled visit will be calculated using the formula below:

$$\% \text{ reduction in PN/IV volume at the visit} = [(\text{average daily value at the scheduled visit} - \text{average daily value at baseline}) / \text{average daily value at baseline}] * 100$$

Document: \\quintiles.net\Enterprise\Apps\sasdata\SASa\sas\Shire\Teduglutide\Biostatistics\Documentation\SAP\TE
D-C14-006_SAP_Final_V1.0_20170714

Author: PPD Version Number: Final V1.0
Version Date: 14Jul2017

Template No: CS_TP_BS016 – Revision 3
Effective Date: 01May2012

Reference: CS_WI_BS005

Copyright © 2012 Quintiles Transnational Corp. All rights reserved.

The contents of this document are confidential and proprietary to Quintiles Transnational Corp. Unauthorized use, disclosure or reproduction is strictly prohibited.

Percent reduction calculation will be performed on both actual and prescribed PN/IV volume data.

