7.6. COMMON CALCULATIONS

For quantitative measurements, change from baseline will be calculated as:

Test Value at Visit X – Baseline Value

Percent change from baseline will be calculated as:

$$\frac{((\text{Test Value at Visit X} - \text{Baseline Value}) / \text{Baseline Value}) * 100}{}$$

Change (or percent change) from baseline tables will be calculated based on the number of subjects in the treatment group with a non-missing value at baseline and at the time point being analyzed.

Document:	\\quintiles.net\Enterprise\Apps\sasdata\SASa\sas\Shire\Teduglutide\Biostatistics\Documentation\SAP\TE D-C14-006_SAP_Final_V1.0_20170714		
Author:	PPD	Version Number:	Final V1.0
		Version Date:	14Jul2017
Template No:	CS_TP_BS016 – Revision 3	Reference:	CS_WI_BS005
Effective Date:	01May2012		

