17.1.2. PRIMARY ANALYSIS OF PRIMARY EFFICACY VARIABLE

Efficacy analyses will be conducted on the ITT and PP set.

The number and percentage of subjects who achieve at least a 20% reduction in weight-normalized average daily actual and prescribed PN/IV volume at EOT will be summarized by treatment arm and dose group. The denominator will be the number of subjects for the population in each treatment arm and dose group.

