17.2. OTHER EFFICACY

17.2.1. OTHER EFFICACY VARIABLES & DERIVATIONS

17.2.1.1. $\geq 20\%$ Reduction in PN/IV volume at each study visit

Similar to the primary analysis, PN/IV volume reduction at each study visit compared to baseline will be calculated. The number and percentage of subjects who achieve at least a 20% reduction in weight-normalized PN/IV volume at each visit during the 24-week treatment period will be summarized by treatment group.

Subgroup analysis by age group and by oral glutamine use will be performed on subject diary data as an exploratory analysis for the ITT analysis set only.

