17.2.1.5. Change and percent change from baseline in enteral nutritional support

The change and percent change from baseline in average daily weight-normalized actual and prescribed EN volume and calories at each post-baseline visit during the 24-week treatment period and 4-week follow-up period will be calculated and summarized using analogous methods as for PN/IV parameters. However, percent change will not be calculated if subject did not take any EN at baseline.

17.2.1.6. Change and percent change from EOT in PN/IV support, citrulline, EN support at EOS

The change from EOT in each parameter or measurement at EOS will be calculated using the formula below:

$$\text{Change from EOT in parameter (or measurement) at EOS} = \text{Value at EOS} - \text{Value at EOT}$$

The percent change from EOT in each parameter or measurement at EOS will be calculated using the formula below:

$$\text{Percent change from EOT in parameter (or measurement) at EOS} = \left[\frac{\text{Value at EOS} - \text{Value at EOT}}{\text{Value at EOT}} \right] * 100$$

If the EOS value is not available, the last non-missing assessment after the EOT will be used as EOS for calculation. If subject has weaned-off PN/IV or EN at EOT, percent change for those parameters will not be calculated.

Document: \\quintiles.net\Enterprise\Apps\sasdata\SASa\sas\Shire\Teduglutide\Biostatistics\Documentation\SAP\TE
D-C14-006_SAP_Final_V1.0_20170714

Author: **PPD** Version Number: Final V1.0
Version Date: 14Jul2017

Template No: CS_TP_BS016 – Revision 3
Effective Date: 01May2012

Reference: CS_WI_BS005

17.2.1.7. Change and percent change from baseline in hours per day and days per week of PN/IV support

Change and percent change of actual and prescribed PN/IV hours per day from baseline to each visit during 24-week treatment period and the 4-week follow-up period will be summarized. These summaries will be presented by treatment arm and dose group using descriptive statistics.

Hours per day of actual PN/IV support for all visits except the baseline visit will be calculated as follows:

Hours per day of actual PN/IV support = (sum of hours per day for each day that PN/IV intake data is recorded within the 7 days prior to the visit / number of days that PN/IV hours per day data is recorded within the 7 days prior to the visit)

Prescribed PN/IV hours per day for each visit (including baseline) will be taken from the most recent prescription data prior to or at that visit.

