17.2.2. ANALYSIS OF OTHER EFFICACY VARIABLES

17.2.2.1. Analysis of All Other Efficacy Variables

Actual and prescribed PN/IV and EN data will be analyzed and summarized separately. However, visit-level listings for average daily weight-normalized PN/IV volume, caloric intake, days per week and hours per day of PN/IV support, will present actual and prescribed data side-by-side.

For the variables of pre-specified % reduction in PN/IV volume, the number and percentage of subjects will be presented by visit and treatment arm and dose group. Baseline values, post-baseline values, change from baseline and percent change from the baseline in PN/IV support will be summarized by visit and treatment arm and dose group using descriptive statistics including number of subjects, mean, standard deviation, median, minimum and maximum.

Document:	\\quintiles.net\Enterprise\Apps\sasdata\SASa\sas\Shire\Teduglutide\Biostatistics\Documentation\SAP\TE D-C14-006_SAP_Final_V1.0_20170714		
Author:	PPD	Version Number:	Final V1.0
		Version Date:	14Jul2017
Template No:	CS_TP_BS016 – Revision 3	Reference:	CS_WI_BS005
Effective Date:	01May2012		

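### SAP 17.1.1 prints the percent-change formula under the name % reduction, so the primary responder variable has the wrong sign for its own cut-off of at least 20%

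*SAP*

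**What the plan says.** SAP 17.1.1 states the endpoint in words: "The primary efficacy variable is weight-normalized reduction in PN/IV volume of at least 20% at EOT compared to baseline". It then gives one formula, labelled as a percent reduction both in the sentence that introduces it and in the formula itself. The numerator reads, typesetting marks included, "average daily value at the scheduled visit} - \text{average daily value at baseline". It is divided by the baseline value and multiplied by 100. The formula applies to both diary (actual) and prescribed volumes.

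The responder rule appears in several places:

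- Section 17 sets the 20% threshold on the "reduction in weight-normalized PN/IV volume between the baseline and week 24/EOT visit".
- Section 17.1.2 counts "subjects who achieve at least a 20% reduction in weight-normalized average daily actual and prescribed PN/IV volume at EOT".
- Section 17.2.1.1 counts "subjects who achieve at least a 20% reduction in weight-normalized PN/IV volume at each visit during the 24-week treatment period".
- Section 17.2.2.1 returns to the same wording: "For the variables of pre-specified % reduction in PN/IV volume, the number and percentage of subjects will be presented by visit".

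Elsewhere the SAP gives this form of expression its usual name. Section 7.6 introduces visit minus baseline, over baseline, times 100 with "Percent change from baseline will be calculated as". Section 17.2.1.6 uses the same form with EOS and EOT values: "The percent change from EOT in each parameter or measurement at EOS will be calculated using the formula below".

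**The concern.** A quantity called a reduction should be positive when PN/IV support falls. The printed one is negative. Set beside a rule that asks for at least 20%, the derivation and the cut-off point in opposite directions. The SAP supplies neither an absolute value nor a threshold of -20% or below to bring them together.

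The place matters more than the slip itself. This is the only printed derivation of the primary efficacy variable. It serves the diary and prescribed analyses, on both the ITT and PP sets, and Section 17.2.1.1 builds the by-visit responder counts on the same calculation. A programmer has to supply a sign that the plan does not state.

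**Working it through.** **Inputs**

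- Formula: SAP 17.1.1, (visit − baseline) / baseline × 100.
- Rule: SAP 17, 17.1.1, 17.1.2 and 17.2.1.1, a reduction of at least 20%.
- Intended range: Protocol 1.3 and 6.1.12, from a 20% fall up to complete weaning.
- Illustrative falls: Protocol 1.1 reports 37% and 39% reductions at Week 12 in the earlier pediatric study, written as positive numbers.

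The plan gives no computed figure to reproduce here, so the check evaluates the formula directly.

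**Algebra**

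Let r = visit / baseline.

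- Printed expression: 100 × (r − 1).
- Reduction: 100 × (1 − r).

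The two have the same size and opposite sign for every r, whatever the baseline volume.

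**Values**

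| Change in PN/IV volume | r | Printed value | Printed value ≥ 20? | True reduction | True reduction ≥ 20? | Printed value ≤ −20? |
|---|---|---|---|---|---|---|
| Complete weaning | 0 | −100 | no | +100 | yes | yes |
| 39% fall | 0.61 | −39 | no | +39 | yes | yes |
| 37% fall | 0.63 | −37 | no | +37 | yes | yes |
| 20% fall | 0.80 | −20 | no | +20 | yes | yes |
| 10% fall | 0.90 | −10 | no | +10 | no | no |
| No change | 1.00 | 0 | no | 0 | no | no |
| 20% rise | 1.20 | +20 | yes | −20 | no | no |
| 30% rise | 1.30 | +30 | yes | −30 | no | no |

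The intended responders run from r = 0.80 down to r = 0. On the printed scale that is −20 down to −100; on a reduction scale it is +20 up to +100. Applying ≥ 20 to the printed value rejects every child whose volume falls and accepts those whose volume rises by 20% or more. The last two columns agree in every row, so either a cut-off of −20 or below on the printed expression, or a reversed numerator with at least 20, gives the intended classification.

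**The case against.** The best reply is that nobody would be misled. In ordinary usage a change of −20% is a 20% reduction, the SAP never writes the inequality ≥ +20 against the computed variable, and the protocol rules out the reverse reading. Section 7.6 already fixes the direction of a signed change, and Section 17.2.1.3 reuses the primary formulas for signed changes in PN/IV volume. On this view the expression is sound and only its name is wrong.

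Much of that stands. The intent is clear, a programmer would probably apply −20 or below, and no misclassification has been shown; the table shells are in a separate file. The analysis is descriptive, without hypothesis tests (SAP 8.4). A reversed sign would also show against the percent-change summaries in 17.2.2.1 and the separate weaning count in 17.2.1.2.

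What does not stand is that the text is therefore adequate. Section 7.6 defines percent change, whereas 17.1.1 calls its quantity a reduction and then requires at least 20% of it. Neither section states the cut-off that would make the two agree.

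**Conclusion.** The label and the formula in SAP 17.1.1 disagree in sign, and the formula as printed does not deliver the stated endpoint. The size is exact: every value is the negative of what its name implies, so the response range reads −20 to −100 instead of +20 to +100. This follows from the algebra alone and rests on no assumption about baseline volume, sample size or response rate.

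The practical risk is low, and no responder count changes if the rule is programmed as intended. Correction is warranted because this is the primary variable's derivation and the cost is trivial. The percent-change summaries in 17.2.1.3 and 17.2.1.5 need the sign as printed and are not in error. The weaning count in 17.2.1.2 does not use the formula.

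**What to change.** Either of two edits is sufficient.

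1. **Keep the formula and correct its name.** In 17.1.1 call the quantity percent change in PN/IV volume and state that a responder has a percent change of −20% or lower. Repeat that definition in 17.1.2 and 17.2.1.1, and align the wording in 17.2.2.1. Leave 17.2.1.3 and 17.2.1.5 as they are. This touches four subsections. The essential edit is the one in 17.1.1; the other three make the definition explicit where responders are counted.
2. **Keep the name and correct the formula.** In 17.1.1 define percent reduction as (baseline − visit) / baseline × 100, with response at 20% or more. Sections 17.2.1.3 and 17.2.1.5 borrow the primary formulas, so point both to Section 7.6; otherwise their percent changes would also reverse sign. This touches three subsections, and 17.2.2.1 can stay.

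Section 17.2.1.6 prints its own formula and needs no edit under either option. The first option is safer, because no borrowed formula changes. Both are SAP wording only, with no change to data or design.

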17.1.2. PRIMARY ANALYSIS OF PRIMARY EFFICACY VARIABLE

Efficacy analyses will be conducted on the ITT and PP set.

The number and percentage of subjects who achieve at least a 20% reduction in weight-normalized average daily actual and prescribed PN/IV volume at EOT will be summarized by treatment arm and dose group. The denominator will be the number of subjects for the population in each treatment arm and dose group.

17.1.3. SENSITIVITY ANALYSIS OF PRIMARY EFFICACY VARIABLE

The same descriptive statistics will also be summarized on investigator prescribed data.

A sensitivity analysis will also be performed using the PP analysis set for both the subject diary data and the investigator prescribed data.

17.2. OTHER EFFICACY

17.2.1. OTHER EFFICACY VARIABLES & DERIVATIONS

17.2.1.1. $\geq 20\%$ Reduction in PN/IV volume at each study visit

Similar to the primary analysis, PN/IV volume reduction at each study visit compared to baseline will be calculated. The number and percentage of subjects who achieve at least a 20% reduction in weight-normalized PN/IV volume at each visit during the 24-week treatment period will be summarized by treatment group.

Subgroup analysis by age group and by oral glutamine use will be performed on subject diary data as an exploratory analysis for the ITT analysis set only.

17.2.1.2. Complete weaning off PN/IV support at EOT

A subject will be considered to have achieved independence from PN/IV support (completely weaned off PN/IV) at EOT if the investigator prescribes no PN/IV at that visit and there is no use of PN/IV recorded in the subject diary during the week prior to EOT.

Document: \\quintiles.net\Enterprise\Apps\sasdata\SASa\sas\Shire\Teduglutide\Biostatistics\Documentation\SAP\TE
D-C14-006_SAP_Final_V1.0_20170714

Author: **PPD** Version Number: Final V1.0
Version Date: 14Jul2017

Template No: CS_TP_BS016 – Revision 3
Effective Date: 01May2012

Reference: CS_WI_BS005

Copyright © 2012 Quintiles Transnational Corp. All rights reserved.

The contents of this document are confidential and proprietary to Quintiles Transnational Corp. Unauthorized use, disclosure or reproduction is strictly prohibited.

The analysis will summarize how many subjects achieve complete weaning of PN/IV support at EOT.

17.2.1.3. Change and percent change from baseline in PN/IV support

Changes in average daily weight-normalized actual and prescribed PN/IV volume at all post-baseline visits during the 24-week treatment period and 4-week follow-up period will be derived using the same formulas as for primary efficacy calculations. Analogous calculations will be used to calculate changes in weight-normalized actual and prescribed PN/IV calories. Mean \pm SE plots of percent change in PN/IV volume (mL/kg/day) and caloric intake (kcal/kg/day) will be generated.

17.2.1.4. Change and percent change from baseline in citrulline

Plasma citrulline levels are measured, collected and transferred by Covance central lab with other lab data. Change and percent change from baseline in plasma citrulline at week 12, week 24 and EOT will be presented by treatment arm and dose group using descriptive statistics.

17.2.1.5. Change and percent change from baseline in enteral nutritional support

The change and percent change from baseline in average daily weight-normalized actual and prescribed EN volume and calories at each post-baseline visit during the 24-week treatment period and 4-week follow-up period will be calculated and summarized using analogous methods as for PN/IV parameters. However, percent change will not be calculated if subject did not take any EN at baseline.

17.2.1.6. Change and percent change from EOT in PN/IV support, citrulline, EN support at EOS

The change from EOT in each parameter or measurement at EOS will be calculated using the formula below:

$$\text{Change from EOT in parameter (or measurement) at EOS} = \text{Value at EOS} - \text{Value at EOT}$$

The percent change from EOT in each parameter or measurement at EOS will be calculated using the formula below:

$$\text{Percent change from EOT in parameter (or measurement) at EOS} = \left[\frac{\text{Value at EOS} - \text{Value at EOT}}{\text{Value at EOT}} \right] * 100$$

If the EOS value is not available, the last non-missing assessment after the EOT will be used as EOS for calculation. If subject has weaned-off PN/IV or EN at EOT, percent change for those parameters will not be calculated.

Document: \\quintiles.net\Enterprise\Apps\sasdata\SASa\sas\Shire\Teduglutide\Biostatistics\Documentation\SAP\TE
D-C14-006_SAP_Final_V1.0_20170714

Author: **PPD** Version Number: Final V1.0
Version Date: 14Jul2017

Template No: CS_TP_BS016 – Revision 3
Effective Date: 01May2012

Reference: CS_WI_BS005

17.2.1.7. Change and percent change from baseline in hours per day and days per week of PN/IV support

Change and percent change of actual and prescribed PN/IV hours per day from baseline to each visit during 24-week treatment period and the 4-week follow-up period will be summarized. These summaries will be presented by treatment arm and dose group using descriptive statistics.

Hours per day of actual PN/IV support for all visits except the baseline visit will be calculated as follows:

Hours per day of actual PN/IV support = (sum of hours per day for each day that PN/IV intake data is recorded within the 7 days prior to the visit / number of days that PN/IV hours per day data is recorded within the 7 days prior to the visit)

Prescribed PN/IV hours per day for each visit (including baseline) will be taken from the most recent prescription data prior to or at that visit.

Days per week of actual PN/IV support for all visits except the baseline visit will be calculated as follows:

Days per week of actual PN/IV support = (number of days with non-zero values for PN/IV volume within the 7 days prior to the visit / number of days for which any PN/IV intake data is recorded within the 7 days prior to the visit) * 7

For the week 1 visit, data prior to the baseline visit will not be used for the calculation.

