4.4 Subject Withdrawal Criteria

All subjects are free to withdraw from participation in this study at any time, for any reason, specified or unspecified. However, a discussion should be held by the investigator and the sponsor's Medical Monitor prior to the patient discontinuing/withdrawing. A subject may (but not automatically) be withdrawn from the study under any of the following circumstances:

- Withdrawal of informed consent and/or assent when applicable
- If, in the opinion of the investigator, Institutional Review Board (IRB) or the sponsor, it is no longer in the subject's best interest to continue in the study
- Subject no longer meets all inclusion criteria or meets any criterion for exclusion
- Lack of compliance with study procedures or study drug administration, as determined by the investigator
- Occurrence of a serious adverse event (SAE) determined by the investigator to be possibly related to study drug and not alleviated with treatment of symptoms
- Adverse event (including Grade 3 or 4 events of special interest [Section 6.1.4])
- Hypersensitivity determined by the investigator to be possibly related to study drug
- Administrative reasons

In all cases, the reason for withdrawal must be recorded in the electronic case report form (eCRF) and in the subject's medical records. If the reason is not known, the subject must be followed-up to establish whether the reason was an AE and, if so, the AE must be reported in accordance with the procedures described in Section 6.1.1. Reasons for discontinuation other than AEs must be reported within 4 weeks of the EOS date in order to be included in the database. Any reason for discontinuation obtained after this time will be included in the

subject's medical record only, unless the EOS visit date is amended and the database remains open.

As far as possible, all examinations scheduled for the EOT evaluations must be performed on all subjects who participate even if they do not complete the study according to the protocol. Any subject who discontinues treatment prematurely will be asked to return 4 weeks later for the EOS visit and will be contacted weekly for wellness checks during the interim period between EOT and EOS.

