8.3 Pharmacodynamic Variables

The following pharmacodynamic parameters will be measured:

- PN/IV volume reduction of at least 20% at 24 weeks (or EOT) compared to baseline

- 100% reduction in PN/IV support (any subjects who are able to completely wean off PN/IV support) compared to baseline at EOT
- Change from baseline (absolute and percent change) in PN/IV support (volume and calories), citrulline, and enteral nutritional support (volume and calories) over time
- Change from Week 24 (or EOT) (absolute and percent change) in PN/IV support (volume and calories), citrulline, and enteral nutritional support (volume and calories) at Week 28 (or EOS)
- Change in body weight, height (or length) and head circumference (up to 36 months of age). Derived variables will include height Z-score, weight Z-score, body mass index (BMI), and BMI Z-score
- Fecal output (by volume or number of bowel movements per day)
- Change in hours per day and days per week of PN/IV support
- Proportion of responders (ie, subjects who achieve at least a 20% reduction in PN/IV volume) over time

Descriptive statistics (mean, median, standard deviation, minimum and maximum values, the number and percentage of subjects in specified categories) will be calculated to summarize the absolute values and change from baseline at each scheduled visit for each treatment group.

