support will be reviewed and adjusted as needed. At the end of the treatment period (week 24/EOT), all subjects will enter a 4-week follow-up period until the end of study (week 28/EOS) during which time no study drug (ie, teduglutide) will be administered. A final visit will be scheduled at week 28, 4 weeks following week 24 or the end of treatment (EOT). Telephone contact will be made during the interim weeks from EOT to end of study (EOS) to monitor safety and any changes in nutritional support.

To maintain consistency across all centers, sites and subjects (randomized and standard of care) should be made to follow the nutritional support adjustment guidelines (developed with SBS expert input and provided in the protocol) for decisions regarding parenteral nutrition/intravenous fluid (PN/IV) support reduction and advances in enteral feeds based on weight gain, urine and stool output, and clinical stability.

Document:	\\quintiles.net\Enterprise\Apps\sasdata\SASa\sas\Shire\Teduglutide\Biostatistics\Documentation\SAP\TE D-C14-006_SAP_Final_V1.0_20170714		
Author:	PPD	Version Number:	Final V1.0
		Version Date:	14Jul2017

[figure not shown]
Template No: CS_TP_BS016 – Revision 3
Effective Date: 01May2012

Reference: CS_WI_BS005

Copyright © 2012 Quintiles Transnational Corp. All rights reserved.

The contents of this document are confidential and proprietary to Quintiles Transnational Corp. Unauthorized use, disclosure or reproduction is strictly prohibited.

Table A Study Diagram

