7.4. WINDOWING CONVENTIONS

Nominal visits will occur within two days of the scheduled week 1 and week 2 visits, within three days of the scheduled week 3 to week 27 visits and within four days of the week 28 (EOS) visit. There will be no windowing of scheduled visits based on study day, and unscheduled visits will not be included in by-visit summaries. Early termination data will be mapped to a scheduled visit if it falls into the appropriate visit window as defined in the protocol and if that scheduled visit did not occur.

An End of Treatment (EOT) time point, defined as the last determination of endpoint or last available measurement after the date of first dose during the 24-week treatment period, will be analyzed in addition to the scheduled visits.

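### A missing Week 28 value is replaced by the last value after end of treatment, so the EOT-to-EOS change can mix different times off drug

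*SAP*

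**What the plan says.** **Endpoint.** Protocol 8.3 lists the change from Week 24 (or EOT) in PN/IV support, citrulline and "enteral nutritional support (volume and calories) at Week 28 (or EOS"). SAP 4.1 fixes the timing: "A final visit will be scheduled at week 28, 4 weeks following week 24 or the end of treatment (EOT"). The interval is meant to be the same after early stopping. Protocol 4.4 says: "Any subject who discontinues treatment prematurely will be asked to return 4 weeks later for the EOS visit", with weekly contacts in between.

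**Fallback.** SAP 17.2.1.6 says: "If the EOS value is not available, the last non-missing assessment after the EOT will be used as EOS for calculation". SAP 7.3 also lets unscheduled measurements contribute to the EOS value. Neither section sets a minimum time off drug or limits which visit may be used. Neither plans an analysis restricted to observed Week 28 values or a count of substitutions.

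**Diary averages.** Under SAP 17.1.1, actual PN/IV and EN values are averaged from subjects' "diaries within 7 days prior to the date of each scheduled post-baseline visit". If more than two of the seven days are missing, "the average daily value will not be calculated and will be assigned as missing". One safeguard separates study periods: "Week 1 calculations will exclude any pre-baseline diary data". No matching rule removes on-drug days from follow-up averages.

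**Schedule.** Protocol Table 6-2 places EOT at day 168, telephone contacts with diary review at days 175, 182 and 189, and EOS at day 196. Over that span citrulline is drawn only at Weeks 24 and 28. The protocol windows are ±2 days for Weeks 24 to 27 and ±4 days for Week 28. SAP 7.4 gives "within three days of the scheduled week 3 to week 27 visits" and four days for Week 28.

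**The concern.** The EOT-to-EOS change is the planned summary that subtracts the end-of-treatment value directly, so it is where a reader will look for what happens when drug stops. Its meaning depends on a common off-drug interval of about four weeks. Because PN/IV and EN data are also reviewed at Weeks 25, 26 and 27, a stand-in will often exist when Week 28 is missing, and it will carry the EOS label although it was measured earlier.

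A second gap compounds this. A Week 25 diary average can include days on drug, because the exclusion at the start of treatment has no counterpart at its end. With a minimum of 10 children per dose arm, a few substituted values can move the arm mean.

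**Working it through.** The plan states no figure for this point, so there is none to reproduce. The check counts days from the schedule.

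**1. Intended interval.** 196 − 168 = 28 days, which agrees with four weeks. With Week 28 at ±4 days, the interval runs from 192 − 170 = 22 to 200 − 166 = 34 days under the protocol's ±2 for EOT, and from 192 − 171 = 21 to 200 − 165 = 35 days under the SAP's ±3.

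**2. Interval that the fallback allows.** The nominal intervals at Weeks 27, 26 and 25 are 21, 14 and 7 days. For Week 25 the window edges give 173 − 170 = 3 days (protocol) or 172 − 171 = 1 day (SAP). An unscheduled assessment has no stated lower limit.

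**3. On-drug days in the Week 25 average.** The window is the seven days strictly before the contact. The last dose is taken to fall on the day of the Week 24 visit, as inferred from the antibody footnote to Protocol Table 6-2. If it fell the day before, each count above zero drops by one.

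- Nominal: diary days 168–174, last dose day 168, so 1 of 7 on drug.
- Protocol ±2, worst case: Week 24 on day 170 and Week 25 on day 173. Diary days are 166–172, so 5 of 7 are on drug. Five recorded days are enough, so the average is wholly on drug if the two off-drug days are missing.
- SAP ±3, worst case: Week 24 on day 171 and Week 25 on day 172. Diary days are 165–171, so 7 of 7 are on drug.
- Of all whole-day date pairs, at least 4 of 7 days are on drug in 3 of 25 (protocol) and 10 of 49 (SAP). These are counts of possible pairs, not probabilities.

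**4. Share of the Week 28 change that a stand-in shows.** Let t be days after EOT. At nominal dates the diary windows are t = 0–6, 7–13, 14–20 and 21–27. For a linear rise the window means are proportional to 3, 10, 17 and 24, so the shares are 3/24 = 12.5%, 10/24 = 42% and 17/24 = 71%. The documents give no off-drug curve, so other assumed shapes are shown alongside:

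| Assumed course after stopping | Week 25 | Week 26 | Week 27 |
|---|---|---|---|
| Linear to day 28 | 12.5% | 42% | 71% |
| Exponential, 7-day time constant | 33% | 78% | 94% |
| Immediate step from day 1 | 86% | 100% | 100% |
| Peak at day 10, half reversed by day 28 | 49% | 146% | 132% |

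**5. Effect on an arm mean.** Assume 10 children with equal true change, m of them replaced by values showing share r. The reported mean is then 1 − (m/10)(1 − r) of the true Week 28 mean. For m = 1, 2, 3:

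- Linear, Week 25 stand-ins: 91%, 83%, 74%.
- Linear, Week 27 stand-ins: 97%, 94%, 91%.
- Early peak, Week 26 stand-ins: 105%, 109%, 114%.

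**The case against.** The strongest reply is that the rule takes the last value. If only the Week 28 diary is too sparse, Week 27 is used; Week 25 enters only when Weeks 26, 27 and 28 are all missing. A mostly on-drug scheduled average also needs a late Week 24 and an early Week 25. Protocol 4.4 brings early stoppers back at four weeks, and no figure in the documents suggests that missing Week 28 data will be common.

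SAP 17.2.1.3, 17.2.1.5 and 17.2.1.7 already plan change from baseline for PN/IV, EN and infusion hours at each follow-up visit. Those summaries use nominal-visit data, and SAP 8.3 says missing data are in general not imputed. An observed Week 28 result will therefore be available as a cross-check. Prescribed values come from the most recent prescription, so sparse diaries and on-drug diary days do not affect them. Citrulline has no scheduled sample between Weeks 24 and 28. Restricting EOS to observed values is not neutral either: it drops children lost after EOT, who may differ from those who stay.

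All of this stands and limits the point. It does not remove it. The by-visit summaries are relative to baseline, so the change from EOT itself is planned only with this rule, with no minimum interval and no report of how often the rule was used.

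**Conclusion.** The point holds in a limited form. The EOS label can cover diary-based PN/IV and EN values taken well short of four weeks off drug, and follow-up averages can include on-drug days: 1 of 7 at Week 25 on nominal dates, up to 5 of 7 (protocol windows) or 7 of 7 (SAP windows) at the edges. The size depends on how many values are substituted, from which week, and on the off-drug course.

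A reader might infer that the rule generally lets one week off drug, or mostly on-drug days, stand for four weeks, and so understates rebound. The documents do not support that. The usual stand-in after a single missed visit is Week 27, and mostly on-drug averages need window-edge dates or an unscheduled assessment. The direction of bias is also open. A Week 25 value falls short under all four assumed curves (12.5% to 86%), but Week 26 and 27 values range from 42% to 146%.

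The primary endpoint is unaffected, citrulline is exposed only through unscheduled samples, and the study is descriptive. The different visit windows may reflect versions: the SAP cites protocol amendment 4, and the protocol at hand is amendment 2. This is a worthwhile, inexpensive clarification of a secondary summary.

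**What to change.** In SAP 17.2.1.6, for the change from EOT to EOS:

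- Use as the main summary only values in the Week 28 window, or four weeks after an early EOT.
- Exclude diary days up to and including the last dose from follow-up averages, mirroring the Week 1 rule.
- Report the number of substituted values and the days off drug for each.
- Keep the last-value fallback as a sensitivity line.

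This needs SAP wording and some programming, but no new data. The cost is a slightly smaller n at EOS. The observed-only summary also omits children lost after EOT; the sensitivity line covers those with any value after EOT.
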